#### 6.5 Safety Assessments

Emergency services (e.g., a crash cart) will be available within the hospital in case of any acute adverse reactions. Adverse events will be monitored during the entire procedure. Specifically, the patient will be monitored with non-leading questions to monitor the patient for the occurrence of transient side effects that are described below.

##### 6.5.1 Risks/Benefits Assessment.

The known risks from the administration of Sonazoid are minimal. Transient side effects that have been described as possibly related to Sonazoid administration include headache (3.6%, 62/1699), chest pain (2.3%, 39/1699), abdominal pain (1.5%, 25/1699), diarrhea (1.5%, 25/1699), and nausea (1.6%, 28/1699).

The majority of adverse events were mild to moderate in severity (92.6%, 652/704).

The use of an intravenous needle and the fluids given through the needle may cause minor discomfort, bleeding under the skin (bruise), and possible infection at the site of needle insertion.

Clinically significant adverse effects from the administration of Sonazoid are unlikely. The use of contrast with the new ultrasound imaging techniques is expected to provide significantly more information than conventional ultrasound techniques. This may lead to a non-invasive method for measurement of hepatic pressure.

To minimize and/or eliminate risks a nurse will be present during the entire procedure. Emergency services (e.g., a crash cart) will be available within the hospital in case of any acute adverse reactions. Adverse events will be monitored during the entire procedure.

The risk benefit ratio is low. Based on the available nonclinical and clinical safety data and the anticipated dose levels of Sonazoid that will be used in this study, safety concerns are minimal. The potential side effects related to Sonazoid administration are described above and listed in greater detail in the investigator's brochure.

#### 6.6.2 Adverse Events (AE)

An AE includes any condition that was not present prior to trial treatment, but appeared following initiation of trial medication; any condition that was present prior to trial treatment, but worsened during trial medication; or any condition, of which the subject has a history, that was not present prior to trial medication initiation but reappeared following administration of Sonazoid. This would include conditions that are likely to be associated with an underlying or intermittent disease (e.g., angina, flu, etc.).

The subjects will be monitored for AEs during the entire procedure. All AEs, including observed or

volunteered problems, complaints, signs or symptoms, and diagnoses, occurring from the initiation of Sonazoid dosing until the completion of the Sonazoid administration will be recorded on a serious or non-serious AE data form, whether or not associated with the use of the trial medication. GEHC will be informed of all AEs. In addition all unexpected and serious adverse events (SAEs) are reported to the TJU or HUP IRB (as applicable) and to the FDA. The investigator is required to submit all unexpected and serious adverse events to the TJU or HUP IRB (as applicable) within 48 hours, and to GEHC. Fatal adverse events related to treatment which are unexpected must be reported within 24 hours to the TJU or HUP IRB (as applicable) and to GEHC. Fatalities not related to the study drug/device must be reported within 5 days. The PI of the study has previous experience running ultrasound clinical trials and will serve as the study sponsor. He will be responsible for ensuring all FDA requirements are met and all AE are properly reported.

The AE forms will include: subject identification number and initials; subject's date of birth, gender, and ethnicity; name of the institution, date of Sonazoid administration; signs/symptoms and severity; date of onset; date of resolution or death; relationship to the study drug; action taken; concomitant medication(s) including dose, and route and duration of treatment.

Whenever possible, the AE will be evaluated and reported as a diagnosis rather than individual signs and symptoms. If a definitive diagnosis is not possible, the individual signs and symptoms will be recorded. The investigator(s) will evaluate and note the duration, intensity, and relationship to (association with) the Sonazoid administration, the action taken, and the determination of seriousness for each AE.

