The proposed agent for the study, Sonazoid (GE Healthcare,), is a sterile non-pyrogenic suspension of lipid stabilized perfluorobutane microbubbles for contrast-enhancement, with a median diameter between 2.4 and 3.5  $\mu\text{m}$  (Forsberg et al. 2008). Previous *in vitro* results have shown Sonazoid to be superior for SHAPE measurements relative to other ultrasound contrast agents (Halldorsdottir et al. 2011). The United States Food and Drug Administration (FDA) has yet to approve Sonazoid for human use in this country. Consequently, we intend to apply to the FDA for an investigator initiated IND (investigational new drug) to cover the use of Sonazoid in patients undergoing a trans-jugular liver biopsy. It should be pointed out that the safety of Sonazoid has already been established in numerous animal studies and in human studies for the evaluation of the liver and heart both in this country and in Europe (Landmark et al. 2008). Sonazoid has been approved for use in patients with liver lesions in Japan and has been marketed in that country since early 2007, and has been approved more recently in South Korea (Bouakaz et al. 2007; Jang et al. 2013). Finally, no adverse reactions attributable to contrast agent infusions were observed in our pilot study (Eisenbrey et al. 2013).

All examinations will be recorded. During the examination, the subharmonic pressure estimates will be

displayed on the Logiq 9 scanner, these estimates will be noted down and the data will be stored on a PC. Data will be compared to the transcatheter portal pressure measurements, which comprise the free and wedged hepatic venous pressure (FHVP and WHVP, respectively) and the hepatic vein pressure gradient (HVPG; measured as the difference between the WHVP and FHVP. Emergency services (e.g., a crash cart) will be available within the hospital in case of any acute adverse reactions. Subjects will be monitored for adverse reactions 2 hours post biopsy (roughly 1 hour post Sonazoid injection), again as a standard of care procedure. Patients will be monitored for a minimum of one hour post Sonazoid administration. During this time a trained CPR personnel and resuscitation equipment will be available. SHAPE data will later be compared to all clinical variables obtained from the patient to determine potential correlations to liver dysfunction.

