## 6.2 Treatment Administration

Administration of Sonazoid will be performed under direct supervision of a medical doctor. Emergency services (e.g., a crash cart) will be available within the hospital in case of any acute adverse reactions. Additionally, resuscitation equipment will be in immediate proximity to the patient during Sonazoid infusion. Patients will be monitored for AEs post Sonazoid treatment for a minimum of one hour. Trained CPR personnel and resuscitation equipment will be in attendance during this monitoring period. A dose of three vials with 48  $\mu$ l of Sonazoid microbubbles (6 ml total after resuspension) will be prepared for each subject by resuspending each vial in 2 ml of injection grade water supplied by GEHC. Infusions will be performed as described in the GEHC protocol supplement (Appendix B), and shown in Figure 1. All materials and supplies used for the infusion procedure will be identical to those described in GE Healthcare's current Sonazoid IND. Briefly, an IV cannula will be placed in a vein in the subject's right arm. A 0.9%NaCl solution will be started and used to fill up the connecting tubes before being connected to a 3-way stopcock. The stopcock will then be connected to the extension tubing leading to the stopcock the cannula. All three vials of suspended Sonazoid will be drawn into a 10 ml syringe, placed in a syringe pump at the same level or below the patient, and connected directly to the stopcock. After the stopcock has been opened, the NaCl solution will be infused at a rate of at least 2 ml/min, and Sonazoid will be infused at the desired rate of 0.024  $\mu$ l/ kg body weight/ minute (suspension infusion rate of 0.18 ml/kg/hour), but may be reduced if necessary to achieve optimal levels of contrast . This infusion rate was selected based on our group's previous experiences with Sonazoid infusion in human subjects in general [Halpern et al. 2002; Landmark et al. 2008] and in SHAPE portal hypertension subjects in particular [Eisenbrey et al. 2013]. This dosing scheme is designed to avoid (or limit) the number of cases that has to be discarded due to insignificant enhancement in the hepatic veins (as in our pilot study; Eisenbrey et al. 2013). This dosage is based off the GEHC instructions for storage and well below the maximal tested dose which was still found safe in Phase I clinical trials (2.7  $\mu$ l of microbubbles/kg in PBI 0001 as detailed in the Sonazoid Investigator's Brochure).

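### The AE-form recording rule in Section 6.6.2 stops when the infusion ends, so AEs first seen in the required hour of post-Sonazoid monitoring need not go on the form

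*Combined protocol and SAP*

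**What the plan says.** Section 6.6.2 states which AEs go on the serious or non-serious AE form, whether or not they are associated with the drug: those "occurring from the initiation of Sonazoid dosing until the completion of the Sonazoid administration will be recorded". The Synopsis (Trial Procedures) plans an infusion of 5 to 10 minutes. Appendix B, Section 6.2, sets a maximum of 15 minutes.

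Monitoring lasts longer. Section 6.2 says "Patients will be monitored for AEs post Sonazoid treatment for a minimum of one hour", and the Synopsis says "Patients will be monitored for a minimum of one hour post Sonazoid administration". Neither sentence is limited to the first exam.

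The AE definition in Section 6.6.2 includes any new condition that arises after trial medication has started, and sets no end time for it. The same section says "GEHC will be informed of all AEs" and asks the investigator to note duration, intensity, relationship, action taken and "the determination of seriousness for each AE". Appendix A, part A, asks for all AEs, including deaths, in the final report to the IRB. None of these duties has a time window.

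**The concern.** The hour after the infusion is there to detect reactions to the agent, but the rule for the AE form ends before that hour begins. A nurse or coordinator who follows the form rule exactly could see an AE during required monitoring, recognise it as an AE under the protocol's own definition, and have no instruction to enter it on the AE form.

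What is at stake is the completeness and consistency of the safety record. With two sites, one may apply the form window literally and the other may record everything seen during monitoring. AE forms and the reports of all AEs to GEHC and the IRB may then disagree. The form fields listed in Section 6.6.2 include a date of onset but no time of onset. For same-day events, those fields would not show which rule a site had applied.

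Sonazoid is described as not FDA-approved. Subjects with portal hypertension receive it again at repeat SHAPE exams over up to 18 months, so the question returns at each exam.

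**Working it through.** This is a check of one rule against others. The plan states no figure on this point to reproduce.

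**Step 1: the two periods.** Count minutes from the start of dosing and let *t* be the infusion time. The form window runs from 0 to *t*. Required monitoring runs to at least *t* + 60.

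- *t* = 5 (planned minimum): form window closes at minute 5, monitoring continues to at least minute 65.
- *t* = 10 (planned maximum): closes at minute 10, monitoring to at least minute 70.
- *t* = 15 (Appendix B maximum): closes at minute 15, monitoring to at least minute 75.

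In each case at least 60 monitored minutes follow the close of the form window.

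**Step 2: can the window sentence be read to include the hour?** No. The Synopsis places the hour after administration ("Patients will be monitored for a minimum of one hour post Sonazoid administration"), so completion of administration cannot mean the end of that hour. For subjects with repeat exams, the window might be read as running from the first infusion to the last. That reading still leaves out the hour after the last infusion, and it does nothing for subjects examined once. No other sentence extends the window.

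**Step 3: trace one event.** Take a new mild headache that starts 30 minutes after a 10-minute infusion ends, which is minute 40. Section 6.5.1 lists headache among the known transient effects.

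- AE definition (6.6.2): met, because it is a new condition after trial medication started.
- Monitoring (6.2, Synopsis): within the required hour.
- Investigator evaluation (6.6.2): due, because it applies to each AE.
- Notice to GEHC (6.6.2): due, because it covers all AEs.
- Final IRB report (Appendix A, part A): due, because it covers all AEs.
- AE form (6.6.2 window): not required.

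The mismatch does not extend to every limb of the definition. The limb on worsening of an existing condition is itself tied to the period of trial medication.

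**Step 4: what is still caught.** Section 6.6.2 gives serious, unexpected and fatal events their own reporting duties with no window. For example, "Fatalities not related to the study drug/device must be reported within 5 days". The Serious Adverse Events text adds medical-monitor review. What remains is mainly non-serious, expected AEs that start after the infusion.

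**Step 5: size.** The Sonazoid Clinical Safety text in Section 1.1 reports that 404 of 1699 subjects (23.8%) had at least one AE, but gives no onset times. Those AEs cannot be split into during and after infusion, so the number of events left off the form cannot be computed.

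**The case against.** The strongest reply is that monitoring and recording are different acts. Section 6.2 governs the first and the window sentence the second. That sentence says AEs during dosing will be recorded; it does not say later ones are excluded. Other text points to wider recording:

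- The form lists date of onset separately from date of Sonazoid administration.
- The relationship assessment goes on a data form.
- Appendix A, part C, puts participants' experiences on CRFs.
- The congenital-anomaly criterion for an SAE applies whenever the diagnosis is made.

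Much of this stands. A reader might infer that the passages flatly contradict each other, or that post-infusion AEs have no route into the record. The documents support neither reading. But these routes do not replace the only sentence that says which AEs go on the AE form.

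Other stronger readings also go too far:

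- One limb of the AE definition covers a past condition "that was not present prior to trial medication initiation but reappeared following administration of Sonazoid". A reader might take this as pointing wholly to the time after the window closes, but it can equally mean after administration has begun.
- The two-hour observation in the Synopsis and Section 3.1 is post-biopsy care. It does not show what happens at repeat exams that follow surveillance imaging. The general one-hour sentences do.
- The one-hour watch in Section 4.2 covers only subjects with non-anaphylactic egg allergy.
- The share of clock time outside the window does not measure lost events.

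It is also fair that no objective or hypothesis concerns safety. That limits the consequence, but it does not make the recording rule sound.

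**Conclusion.** The point holds as a mismatch. The form rule ends with the infusion, after 5 to 10 minutes as planned and 15 at most, while required monitoring continues for at least another hour and the duties to evaluate and report cover all AEs. Following the form rule as written gives a less complete AE record than the plan's own monitoring could supply.

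The likely loss is mainly of non-serious, expected AEs first seen after the infusion. Its size is unknown, for want of onset times. Bedside observation, the separate duties for serious, unexpected and fatal events, and the accuracy analyses are not affected.

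The conclusion rests on reading completion of administration as the end of the infusion, which the Synopsis supports, and on staff applying the form rule literally. It is worth correcting because the correction is specific and cheap.

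**What to change.** Reconcile Section 6.6.2 with Section 6.2 and the Synopsis by changing the recording rule in 6.6.2 and adding a matching line to the AE form:

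- Run the form window from the start of Sonazoid dosing to the end of the post-Sonazoid monitoring already required, at the baseline exam and at every repeat SHAPE exam.
- State that any later AE that becomes known and is reported to GEHC or the IRB, including any serious, unexpected or fatal event, is also entered on the form. Without this second part, an AE starting after the monitored hour would still fall within the reports of all AEs yet stay off the form.

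The change takes one or two sentences and adds no observation, because the monitoring is already required. The drawback is a somewhat higher recorded AE count, including events caused by the biopsy. The existing relationship assessment classifies those, and 6.6.2 already records AEs whether or not they are associated with the drug.

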#### INTENSITY OF AEs

The intensity of the AE will be characterized as mild, moderate, or severe.

Mild AEs are usually transient, require no special treatment, and do not interfere with the subject's daily activities.

Moderate AEs traditionally introduce a low level of inconvenience or concern to the subject and may

interfere with daily activities but are usually ameliorated by simple therapeutic measures.

Severe AEs interrupt a subject's usual daily activity and typically require systemic drug therapy or other treatment.

When the intensity of the AE changes over time, the maximum intensity will be recorded.

## RELATIONSHIP TO SONAZOID ADMINISTRATION

The relationship or association of the AE to the Sonazoid administration will be characterized as "unlikely," "possible," or "probable." A relationship assessment will be performed by the investigator to determine if an AE is attributable to Sonazoid and will be recorded on a data form. The investigator will refer to the Sonazoid investigator brochure for assistance in determining AE relationship.

An "unlikely" relationship indicates that there is little or no chance that Sonazoid caused the reported AE; other conditions, including concurrent illnesses, progression or expression of the disease state, or a reaction to a concurrent medication, appear to explain the reported AE.

A "possible" relationship indicates that the association of the AE with Sonazoid is unknown. However, the AE is not reasonably attributed to any other condition.

A "probable" relationship indicates that a reasonable temporal association exists between the AE and Sonazoid administration and, based upon the investigator's clinical experience, the association of the event with the trial medication seems likely.

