**Trial Procedures:** Subjects eligible for trial enrollment will be identified by the co-investigators, [name] (at TJU) and [name] (at HUP) from their patient population of subjects scheduled for a trans-jugular liver biopsy. The research coordinators for this study will explain the study to the patients at the respective clinical sites. The patient will be given time to consider the risks and benefits of the study and ask questions about participation. The coordinator will review the consent form with the patient and then the patient will be given the form to review. The patient, coordinator, and a study investigator will all sign the consent form. The patient will be given a copy of the signed consent form for their records.

After consenting to participate in this study, a full demographic profile, known drug allergies or intolerances, and review of the subject's medical/surgical history will be recorded. Patients with known cardiac shunts will be excluded from the study. If the subject is a woman of childbearing potential, she will have a urine pregnancy test (the results of which will be made available to the subject prior to study initiation).

Whenever a subject undergoes a trans-jugular liver biopsy with transcatheter free and wedged hepatic venous pressure measurements as part of their standard clinical care and agrees to participate in the study, we will perform the corresponding SHAPE measurement within the 3 hours of post-recovery observation to ease transportation for patients and ensure that hydration status and other variables, which could potentially affect portal pressures, are equivalent. Administration of Sonazoid will be performed under

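### An adverse event of uncertain cause that has a reasonable alternative explanation fits none of the three causality labels and will probably be filed as 'unlikely'

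*Combined protocol and SAP*

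**What the plan says.** The subsection on relationship to Sonazoid administration, within Section 6.6.2 of the combined protocol and SAP, offers three labels.

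- *Unlikely*: this "relationship indicates that there is little or no chance that Sonazoid caused the reported AE". The definition continues that other conditions, such as concurrent illness, "progression or expression of the disease state, or a reaction to a concurrent medication, appear to explain the reported AE".
- *Possible*: this "relationship indicates that the association of the AE with Sonazoid is unknown". A second sentence then restricts it: "However, the AE is not reasonably attributed to any other condition".
- *Probable*: the timing is reasonable and, in the investigator's experience, "the association of the event with the trial medication seems likely". Nothing is said about other causes.

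On setting, the Synopsis (Trial Procedures) says that after a transjugular biopsy "we will perform the corresponding SHAPE measurement within the 3 hours of post-recovery observation". Section 3.1 puts the imaging within two hours of the biopsy.

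On reporting, Section 6.6.2 says: "Fatal adverse events related to treatment which are unexpected must be reported within 24 hours" to the IRB and the supplier. Deaths not related to the drug or device have 5 days. Unexpected serious events go to the IRB within 48 hours, with no condition on relatedness. The AE form carries a field for relationship to the study drug.

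**The concern.** A causality scale should give every event one label, and the labels should rise in order of suspicion. Here the middle label is stricter about alternative causes than the top one. An investigator who is unsure about Sonazoid, and who can also see another reasonable explanation, has no label that fits.

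That is an ordinary situation in this trial. The patients have liver disease, and at the index examination they have just had a biopsy. The side effects listed for Sonazoid in Section 6.5.1 are non-specific: headache, chest pain, abdominal pain, diarrhea and nausea. If such events settle in *unlikely*, the relationship field understates possible relatedness. A death in this group could also leave the 24-hour reporting route.

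**Working it through.** The documents state no figure that depends on this scale, so the check is one of logic. Cross the investigator's view of Sonazoid as a cause with whether the event is reasonably attributed to something else, and apply each definition literally.

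| View of Sonazoid as cause | Reasonable alternative: yes | Reasonable alternative: no |
|---|---|---|
| Little or no chance | *Unlikely* (both clauses met) | *Unlikely* on its first clause only |
| Unknown | **No label fits** | *Possible* |
| Likely, timing reasonable | *Probable* | *Probable* |

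For the cell in bold:

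1. *Possible* is barred by its second sentence.
2. *Probable* is not met, because the link is not judged likely.
3. *Unlikely* is not met, because an unknown association is not the same as next to no chance.

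Of the three, *unlikely* has the only wording that matches part of the case: another condition appears to explain the event. It is therefore the natural default, although the text does not assign the event there.

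**When the cell arises.** The Synopsis ties a Sonazoid infusion to each transjugular biopsy, so index examinations and biopsy-triggered repeats fall within hours of one. Repeats tied to six-monthly surveillance imaging do not follow a biopsy, though underlying liver disease can still compete as an explanation. Section 1.1 (Sonazoid Clinical Safety) gives adverse event rates of 404/1699 = 23.8% on Sonazoid and 12/62 = 19.4% on placebo. The placebo group is small, but with rates this close the cause of a single event will often be uncertain.

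**What depends on the label** (Section 6.6.2 and the subsection on serious adverse events):

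| Step | Depends on relatedness? |
|---|---|
| Recording the event | No |
| Informing the supplier of AEs | No |
| IRB report of unexpected serious events, 48 hours | No |
| Relationship field on the AE form | Yes |
| Clock for deaths, 24 hours or 5 days | Yes |

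**Size of the timing effect.** An unexpected death judged related has 24 hours. If it is judged unrelated, the 5-day rule (5 × 24 = 120 hours) and the 48-hour rule both apply on their face, and Section 6.6.2 does not say which governs. The extra time is therefore 48 − 24 = 24 hours or 120 − 24 = 96 hours.

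**Missing link.** The reporting rules use a two-way split, related or not related, while the scale has three labels. Nothing says on which side *possible* falls.

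**The case against.** The strongest case against is that this is a small wording gap with several safeguards around it.

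- *Possible* is closed only when the event is reasonably attributed to another condition. That is a case-by-case judgement made with the investigator's brochure; a recent biopsy does not by itself explain a headache.
- Symptoms already present and unchanged when Sonazoid starts are not AEs under Section 6.6.2.
- The medical monitor gives a separate opinion on relationship for serious and unexpected events.
- No planned analysis in Section 7.2 tabulates AEs by relatedness.

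All of this stands, and it limits the consequence. It does not close the gap. The monitor's report may come up to 10 calendar days after the initial report, later than any of the clocks above, and it does not cover non-serious events.

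A reader might infer more than the documents support, in three ways.

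- *That nearly every reaction with a competing explanation is pushed to unlikely.* The text does not do this. *Unlikely* keeps its own demanding first clause, and *probable* stays open whenever the investigator thinks the link likely.
- *That the number affected can be estimated as 300 × 404/1699, about 71 patients.* That figure counts patients with any AE, not misclassified events. It also borrows rates from trials whose collection windows are not given, whereas Section 6.6.2 records AEs only from the start to the completion of administration, an infusion of 5 to 10 minutes. Those rates include laboratory and ECG findings, for which this protocol schedules no safety tests.
- *That a death simply moves from 24 hours to 5 days.* The 48-hour rule also applies on its face to an unexpected death.

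**Conclusion.** The defect is real and narrow. The three definitions are not exhaustive: uncertain causality together with a reasonable alternative explanation has no label. The likely default is *unlikely*, so the error tends to run towards understating possible relatedness. The default is a judgement about how investigators will use the form, not something the text directs.

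The consequence is confined to the relationship field of the AE form, any later summary drawn from it, and the clock for fatal events, where the added time is 24 or 96 hours depending on which rule governs. The number of events affected cannot be computed from the documents. The conclusion assumes that effects of the biopsy and of the underlying liver disease count as other conditions under the scale, which is the natural reading.

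It is worth correcting: the faulty rule is explicit, the situation it mishandles can be expected at index and biopsy-triggered examinations, and rewording is cheap.

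**What to change.** Amend the relationship definitions and the AE form instructions as follows.

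1. *Possible*: there is a reasonable temporal association with Sonazoid and the link is not judged likely enough for *probable*. The event could also be explained by the biopsy, the underlying disease or another medication, but such an explanation neither is required nor rules the label out.
2. *Unlikely*: keep for events with little or no chance of a Sonazoid cause. The mere presence of another explanation is not enough.
3. *Probable*: no change needed.
4. In Section 6.6.2, state that *possible* and *probable* both count as related for the reporting rules, and say whether the 48-hour or the 5-day rule governs an unexpected death judged unrelated.

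The cost is a few sentences in the protocol and the form instructions. The downside is small: more events will be labelled possibly related, and some fatal events will be reported on the faster clock. No change to data collection or sample size is needed.
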